6.1 Design description

This is a prospective, open-label, multicentre, randomized investigation to evaluate the effectiveness, safety and long-term safety of Saypha® FILLER Lidocaine for bilateral lip augmentation and to assess the duration of the aesthetic effect of the device. As justified in section 3.3, this type of design is considered appropriate in view of the purpose and objectives of the study.

The investigation comprises of six on-site visits within 18 months (76 weeks):the Screening/Baseline visit (Visit 1/Day 0) and 5 follow-up visits at 3 weeks (Visit 2), 6 weeks (Visit 3), 6, 12, and 18 months after initial treatment (Visits 4, 5 and 6). Visit 6 at Month 18 is an optional visit. In case it is observed by the investigator at the 12 months visit (Visit 5) that no aesthetic effect is any more visible the study can be terminated at Visit 5. Subjects will randomly be assigned to one of the two IMDs at a 1:1 ratio ('IMD-HQ': 'IMD-C1').

The Screening/Baseline visit (Visit 1) will entail informed consent and screening assessments as specified in section 6.5.1. During this visit the investigator will determine the inclusion of subjects based on inclusion/exclusion criteria (see sections 6.3.3 and 6.3.4).

Eligible subjects will be randomized to one of the IMDs ('IMD-HQ' or 'IMD-C1') and undergo bilateral lip augmentation treatment with Saypha® FILLER Lidocaine in order to correct moderate to severe deficiency of lip volume at Visit 1 (Day 0). In addition to this initial treatment an optional touch-up treatment can be performed at Visit 2 (Week 3) in order to achieve optimal cosmetic corrections (in the discretion of the investigator). The injection volume will be recorded at each treatment visit (i.e., Visit 1 and Visit 2) (see section 6.4.6). 24 hours after each treatment a telephone visit will be performed for safety evaluation (Visit 1a and Visit 2a in case of touch-up treatment; see sections 6.5.2 and 6.5.4).

Baseline severity of lip volume deficiency will be determined at Visit 1 by the investigator using a validated 5-point Lip Fullness Scale (LFS) before the initial treatment. The LFS will be repeated 6 weeks and 6, 12 and optional 18 months after the initial IMD treatment. Independent photographic reviews will be performed at the same time points using LFS on photographs (see section 6.4.7).

Subject's pain during treatment and recovery from treatment will be evaluated by means of a numerical pain rating scale (NPRS) immediately and 15 minutes after each IMD administration (see section 6.4.8).

Global aesthetic improvement (GAIS) relative to baseline photographs will be evaluated by both - the investigator and the subject - at 6 weeks and 6, 12 and optional 18 months after initial IMD treatment (see section 6.4.9).

Subject's satisfaction with the outcome of the treatment will be assessed with the Face-QTM questionnaires "Satisfaction with Outcome" (see section 6.4.10) and "Satisfaction with Lips" (see section 6.4.11) at 6 weeks and 6, 12 and optional 18 months after initial treatment.

Assessment of the aesthetic effect of injection of Saypha® FILLER Lidocaine will be performed by the investigator at 6 weeks and 6, 12 and optional 18 months after initial treatment (see section6.4.12).

The safety will be evaluated based on occurrence of adverse events, which will be collected at each visit throughout the clinical investigation, beginning immediately after start of initial treatment until the last visit. In order to identify potential adverse events post-administration a safety evaluation after 15 minutes needs to take place (see section 6.4.13).

A detailed schedule of procedures is given in section 6.5 and Table 1; Description of assessments can be found in section 6.4.

6.1.1 Criteria for evaluation (endpoints)

Primary performance endpoints

The performance of the investigational device will be evaluated using the following primary endpoint (justification is provided in section 3.3):

The proportion of subjects ('responders') with the lip volume improved by ≥1 point versus baseline
value at 6 weeks after initial treatment based on the investigator live assessment using the
validated Lip Fullness Scale (LFS).

'Responder' is defined having at least ≥ 1 grade improvement as evaluated with the 5 point-validated LFS at a given visit relative to Baseline score. Individual LFS grades per visit will be calculated separately for the upper and the lower lip.

Safety endpoints

The safety of the investigational device will be evaluated using the following endpoint:

Occurrence and frequency of adverse events

Secondary performance endpoints

- The percentage of responders, based on the investigator live assessment at 6, 12 and optional 18 months after the initial treatment using the validated LFS.
- The percentage of responders based on the independent photographic reviewer's assessments before initial treatment and at Week 6, Month 6, 12 and optional Month 18 after initial treatment, based on photographs and using the validated LFS.
- The percentage of subjects with an improvement relative to baseline photographs, (subjects who have been rated as "very much improved" or "much improved" or "improved"), based on the investigator assessment at Week 6, Month 6, 12 and optional Month 18 after initial treatment using the 5-point GAIS.
- The percentage of subjects with an improvement relative to baseline photographs (subjects who have been rated as "very much improved" or "much improved" or "improved"), based on subject assessment at Week 6, Month 6, 12 and optional Month 18 after initial treatment, using the 5-point GAIS.
- The extent of subject's satisfaction with overall outcome of the treatment, at Week 6, Month 6, 12 and optional Month 18 after initial treatment, assessed by the subject using the Face-QTM Questionnaire "Satisfaction with Outcome".
- The extent of subject's satisfaction with augmentation of lips, at Week 6, Month 6, 12 and optional Month 18 after initial treatment, assessed by the subject using the Face-QTM Questionnaire "Satisfaction with Lips".
- Subject's perception of pain after initial and touch-up treatment with Saypha® FILLER Lidocaine
 using the 11-point Numeric Pain Rating Scale (NPRS), where 0 is no pain and 10 is the worst pain
 imaginable.
- Percentage of subjects demonstrating an aesthetic effect at Week 6, Month 6, 12 and optional Month 18 based on the investigator's life assessment.
- Injection volume (initial and touch-up) required for an optimal augmentation of the lips with Saypha® FILLER Lidocaine.

6.1.2 Randomization

Subjects providing written informed consent and having met all inclusion and none of the exclusion criteria will be randomized in a 1:1 ratio to one of the two IMDs (either IMD from manufacturing site 'HQ' or 'C1') (see section 2.2 for details). The site staff can perform the randomization via the eCRF sytem and distribute the respective IMD ('IMD-HQ' and 'IMD-C1') to the subjects accordingly.

6.1.3 Blinding

Not applicable.

6.1.4 Discussion of clinical investigation design

This clinical investigation is undertaken to evaluate the effectiveness, safety and long term safety of Saypha® FILLER Lidocaine for lip augmentation and to assess the duration of the aesthetic effect after implantation.

The primary and one of the secondary performance endpoints (see section 6.1.1) is based on the 5-grade LFS (Lip Fullness Scale), a validated instrument for semi-quantitative assessment of lip fullness (see section 6.4.7). Difference of one grade on this scale is considered to be clinically meaningful since it can be visually recognized by various observers as demonstrated during validation of the scale.

In view of multicenter conduct of the investigation, the LFS assessment will be also evaluated centrally, by an experienced independent photographic reviewer (see section 6.4.7). This will allow for unified assessment of treatment responses across the sites and checking if any bias was introduced by inter-observer variability between the sites.

The clinical relevance of the investigation will be also supported by several secondary endpoints (see section 6.1.1), related to global aesthetic improvement (by using the GAIS) and subject's satisfaction with outcome (overall and the lips by using Face-QTM scales).

A randomization to IMD produced by one of the manufacturing sites 'HQ' and 'C1' will be done. It shall be shown that there is no difference in effectiveness and safety of the two IMDs between the two manufacturing sites.

Safety and long term safety of Saypha® FILLER Lidocaine for lip augmentation will be monitored by documentation of safety parameters (AEs and device deficiencies) (see section 6.4.13).

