5.1 Objectives

The main objectives of this investigation are:

- To evaluate the effectiveness, safety and long-term safety of Saypha® FILLER Lidocaine for lip augmentation;
- To assess the duration of the aesthetic effect of Saypha® FILLER Lidocaine for lip augmentation.

Additional objectives:

- To compare the effectiveness of Saypha® FILLER Lidocaine ('IMD-HQ' and 'IMD-C1') produced in the two different manufacturing sites ('HQ' and 'C1').
- To compare the IMD injection techniques 'retrograde technique' and 'bolus technique'
- To compare the injection equipment used: '27G ½" needle' versus cannula ('25G x 50mm cannula' or '22G x 70mm cannula')

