5.2 Hypotheses

This is a non-comparative study and does not entail formal hypothesis testing.

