7.3.2 Final analysis

Final analysis will be done after completion of the investigation by all subjects. All primary, secondary and safety endpoints will be tabulated by visit, if applicable, and summarized using descriptive statistics only. The final analysis will be done for the 'overall population' and for several defined subgroups (see section 7.3.10 for more information).

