7.3.10 Analysis of subgroups

Besides the 'overall population' (including all subjects enrolled in the investigation), which includes all enrolled subjects, the following subgroups will descriptively be analyzed:

IMD from manufacturing sites: 'HQ' and 'C1'

In this study, IMD from two different manufacturing sites ('C1' and 'HQ') will be used and subjects will be randomly assigned in a 1:1 ratio to 'IMD-C1' or 'IMD-HQ', respectively.

This subgroup analysis will compare both IMDs ('IMD-HQ' or 'IMD-C1') and separately analyze the results for the 'IMD-C1' and 'IMD-HQ' subgroups.

• Injection technique: 'retrograde technique' and 'bolus technique'

It is planned to descriptively analyze the performance of the IMD separated by injection technique.

The corresponding subgroup analysis will separately analyze the results for subjects treated with the two different injections techniques.

• Injection equipment: '27G ½" needle' versus cannula ('25G x 50mm cannula' or '22G x 70mm cannula')

It is planned to analyze the performance of the IMD separately for the injection equipment used (27G $\frac{1}{2}$ " needle versus cannula (25G x 50mm cannula or 22G x 70mm cannula)). Therefore it is planned to treat a minimum of 30 subjects either with needle or cannula (25G x 50mm cannula or 22G x 70mm cannula).

The corresponding subgroup analysis will separately analyze the results for subjects treated by means of the different injection equipment.

All subgroup analyses are planned to be performed for the primary performance endpoint and the main secondary performance endpoints.

The following secondary performance endpoints are planned to be analyzed:

- The percentage of responders, based on the investigator live assessment at 6, 12 and optional 18 months after the initial treatment using the validated LFS.
- The percentage of responders based on the independent photographic reviewer's assessments before initial treatment and at Week 6, Month 6, 12 and optional Month 18 after initial treatment, based on photographs and using the validated LFS.
- The percentage of subjects with an improvement relative to baseline photographs, (subjects who
 have been rated as "very much improved" or "much improved" or "improved"), based on the
 investigator assessment at Week 6, Month 6, 12 and optional Month 18 after initial treatment using
 the 5-point GAIS.
- The percentage of subjects with an improvement relative to baseline photographs (subjects who

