9.6 Sample Size Calculation

Confidence Interval calculation has been performed for the primary performance endpoint “The proportion of subjects ('responders') with the lip volume improved by ≥ 1 point versus baseline value at 6 weeks after initial treatment based on the investigator live assessment using a validated Lip Fullness Scale (LFS)”. A responder is defined having at least ≥ 1 grade improvement compared to baseline values on the 5 point-validate lip fullness scale”.

Approximately 110 subjects with moderate to severe volume deficiency of lips will be enrolled in order to obtain performance and safety data.

This sample size is arbitrarily selected and is considered sufficient to provide robust estimations on performance and safety parameters in the overall study population and in the subgroups regarding IMD manufacturing site. With a sample size of 100, a two-sided 95% confidence interval for a single proportion using the large sample normal approximation will extend by 0.059 in the overall population and 0.083 in the two manufacturing site subgroups from the observed proportion for an expected proportion of 0.900 (i.e., responder rate of 90%; calculated with nQuery Advanced 8.2.1.0). In order to cover subjects’ drop-out or

lost to follow-up the sample size will be increased by 10%. 110 subjects will be enrolled (with 55 subjects per manufacturing site). Thus, a robust estimation of the success rate at week 6 can be derived.

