9.8 Final Analysis

Final analysis will be done after completion of the investigation by all subjects. All primary, secondary and safety endpoints will be tabulated by visit, if applicable, and summarized using descriptive statistics only. The final analysis will be done for the 'overall population' and for several defined subgroups.

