10.8 Subgroup Analyses

Besides the ‘overall population’ (including all subjects enrolled in the investigation), which includes all enrolled subjects, the following subgroups will descriptively be analyzed:

- **IMD from manufacturing sites: ‘HQ’ and ‘C1’**
 IMD from two different manufacturing sites (‘C1’ and ‘HQ’) will be used and subjects will be randomly assigned in a 1:1 ratio to ‘IMD-C1’ or ‘IMD-HQ’, respectively.
 Subgroup analysis will compare both IMDs (‘IMD-HQ’ or ‘IMD-C1’) and separately analyze the results for the ‘IMD-C1’ and ‘IMD-HQ’ subgroups.
 Summary of subgroup analysis will compare both IMDs (‘IMD-HQ’ or ‘IMD-C1’) will be analyzed descriptively using FAS populations
- **Injection technique: ‘retrograde technique’ and ‘bolus technique’**
 Subgroup analysis will separately analyze the results for subjects treated with the two different injections techniques.
 Summary of different injections techniques will be analyzed descriptively using FAS populations
- **Injection equipment: ‘27G ½” needle’ versus cannula (‘25G x 50mm cannula’ or ‘22G x 70mm cannula’)**
 Subgroup analysis will separately analyze the results for subjects treated by means of the different injection equipment.
 All subgroup analyses are planned to be performed for the primary performance endpoint and the main secondary performance endpoints.

All subgroup analyses are planned to be performed for the primary performance endpoint and the main secondary performance endpoints using FAS population only.

The following secondary performance endpoints are planned to be analyzed:

- The percentage of responders, based on the investigator live assessment at 6, 12 and optional 18 months after the initial treatment using the validated LFS.

- The percentage of responders based on the independent photographic reviewer’s assessments before initial treatment and at Week 6, Month 6, 12 and optional Month 18 after initial treatment, based on photographs and using the validated LFS.
- The percentage of subjects with an improvement relative to baseline photographs, (subjects who have been rated as “very much improved” or “much improved” or “improved”), based on the investigator assessment at Week 6, Month 6, 12 and optional Month 18 after initial treatment using the 5-point GAIS.

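### The protocol promises to show that HQ and C1 product do not differ in effectiveness and safety, but neither document plans an analysis that could show it

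*Protocol*

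**What the plan says.** Protocol 6.1.4 gives the purpose of randomising to product from the two manufacturing sites: "It shall be shown that there is no difference in effectiveness and safety of the two IMDs between the two manufacturing sites". This covers both effectiveness and safety.

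Elsewhere the plan is more modest:

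- Protocol 5.1 lists, as an additional objective only, "To compare the effectiveness of Saypha® FILLER Lidocaine" from the two sites. Safety is not part of that objective.
- Protocol 5.2: "This is a non-comparative study and does not entail formal hypothesis testing".
- Protocol 7.3.10: "This subgroup analysis will compare both IMDs". The subgroups are, however, to be analysed descriptively, with results given separately for each device.
- SAP 10.8 repeats this and restricts it: "All subgroup analyses are planned to be performed for the primary performance endpoint and the main secondary performance endpoints using FAS population only". The endpoints listed are LFS responders (live and photographic), GAIS and NPRS pain. Adverse events are not listed.
- SAP 9.6 gives precision as "0.083 in the two manufacturing site subgroups from the observed proportion for an expected proportion of 0.900".

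On safety, protocol 7.3.2 says "All primary, secondary and safety endpoints will be tabulated by visit, if applicable, and summarized using descriptive statistics only", and SAP 9.8 runs the final analysis for the overall population "and for several defined subgroups". SAP 9.2 assigns wrongly treated subjects in the SAF to the device they received first. SAP 10.7.1 specifies no adverse event table by device. Its limit to the overall population is attached only to the overview table.

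**The concern.** Showing that two products do not differ needs an estimate of the difference, its uncertainty and, for a positive claim, a margin. The plan has none of these. It names two tests: a one-sample binomial test against 0.900 (SAP 10.6.1) and a paired t-test on pain (SAP 10.6.2). Neither compares the devices. Two similar arm percentages could therefore be reported as fulfilling 6.1.4 when the data remain compatible with a sizeable gap.

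The comparison matters. According to protocol 2.2, HQ is the new site, process parameters were adapted during the transfer, most equipment is new, and the HQ material is not CE-certified. Protocol 4.5 assumes in advance that the new site has no impact on safety or effectiveness. Section 6.1.4 is where the trial undertakes to show it. For safety, whether and how adverse events will be shown by device is left to interpretation.

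**Working it through.** **Inputs.** Responder rate 0.90; 100 evaluable subjects, hence 50 per arm at 1:1; 110 enrolled, 55 per arm (protocol 7.1, SAP 9.6). Adverse device effect (ADE) incidences: 26/60 = 43.3% in the nasolabial fold study of this device (protocol 4.2.2) and 5/53 = 9.4% in the study of the filler without lidocaine (protocol 4.2.1). Both come from other indications, so they are an assumed range.

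**1. The plan's own figures.** Half-width = 1.96·√(p(1−p)/n).
- n = 100: 1.96·√(0.09/100) = 0.059
- n = 50: 1.96·√(0.09/50) = 0.083

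Both are reproduced. Both describe a single proportion.

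**2. Interval for HQ minus C1 at 0.90 in both arms, 50 per arm.**
- Wald: 1.96·√(2·0.09/50) = 0.118
- Newcombe: the Wilson limits for 45/50 are 0.786 and 0.957, so the half-width is √((0.900−0.786)² + (0.957−0.900)²) = 0.127
- Miettinen-Nurminen: 0.132

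Identical observed rates would thus leave a gap of about 13 points in either direction inside the interval.

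**3. Dependence on the responder rate (Newcombe, equal rates, 50 per arm).**

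| Rate in both arms | Half-width |
|---|---|
| 0.80 | 0.157 |
| 0.85 | 0.144 |
| 0.90 | 0.127 |
| 0.95 | 0.104 |

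**4. A visible gap.** Observed 45/50 v 40/50 gives a difference of 0.10, with Newcombe interval −0.043 to 0.242 (Wald −0.039 to 0.239).

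**5. How often a real gap would show.** Summing over both binomial distributions with 50 per arm, the probability that the Newcombe 95% interval excludes zero is:

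| True rates | Probability |
|---|---|
| 0.90 v 0.80 | 0.27 |
| 0.90 v 0.75 | 0.50 |
| 0.90 v 0.70 | 0.72 |

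**6. Safety, 55 per arm, equal incidences.**
- 43.3%: Newcombe ±0.179; Wald 1.96·√(2·0.433·0.567/55) = ±0.185; Miettinen-Nurminen (24/55 in both arms) ±0.182
- 9.4%: Newcombe ±0.118; Wald 1.96·√(2·0.094·0.906/55) = ±0.109; Miettinen-Nurminen (5/55 in both arms) about ±0.116

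**7. What a margin would require.** The documents give none, so these margins are assumptions. SE = √(2·0.09/50) = 0.06, true difference zero. Non-inferiority power is Φ(margin/SE − 1.96). The power to have the whole 95% interval inside ±margin is 2Φ(margin/SE − 1.96) − 1, or 0 where that is negative.

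| Margin | Non-inferiority | Interval inside ±margin |
|---|---|---|
| 10 points | 39% | about 0% |
| 15 points | 71% | 41% |
| 20 points | 92% | 83% |

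**The case against.** The conflict rests on one sentence in a discussion section. The objectives, the hypotheses section and the analysis sections are consistently descriptive, and the SAP never repeats the promise. The 0.083 is correctly labelled as a single-proportion width. Protocol 7.3 plans 95% intervals for responder percentages, so a reader could derive the difference and its interval. On safety, protocol 7.3.2, SAP 9.8 and the SAF rule in SAP 9.2 together suggest that a display by device is intended. A justified margin would be another legitimate way to keep the aim. The 0.90 v 0.80 scenario is one choice among several, and the chance of excluding zero is not itself a measure of support for no difference.

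Much of this is fair, and it limits the point to a stated aim outside the primary single-group estimate. It does not remove the point. The 6.1.4 sentence is current protocol text and gives the reason for randomising. An interval that readers must build themselves is not prespecified, and nothing ties the conclusion to it. The generic line in protocol 7.3 on two-sided tests at 0.05 is not linked to this comparison, and a non-significant result would not show equality. For safety, SAP 10.8 confines subgroup analyses to performance endpoints in the FAS, so the ambiguity is real. A margin remains possible in principle, but at 50 per arm it would have to be near 20 points to give a good chance of success.

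**Conclusion.** The concern holds. Followed as written, the plan cannot support the conclusion that protocol 6.1.4 commits to. For effectiveness, the between-device 95% interval would be about ±0.13 with 50 evaluable per arm and 90% response in both, against the stated one-arm 0.083; it ranges from ±0.104 to ±0.157 for common rates of 0.95 down to 0.80. For safety, it would be about ±0.12 to ±0.18 with 55 per arm, assuming ADE incidences between 9.4% and 43.3%. That range is borrowed from other indications, and its lower end comes from the filler without lidocaine. The overall responder estimate is unaffected.

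**What to change.** 1. **SAP 10.8.** Report HQ minus C1 in Week 6 responder rate with a 95% Newcombe or Miettinen-Nurminen interval. Show the live and photographic LFS results side by side, because investigators can tell the two devices apart (protocol 6.2.1) and both are already by-device endpoints. Use the same unit of analysis as the primary endpoint, once protocol 6.1.1 and 7.3.7 (lips separately) are reconciled with protocol 7.3 (mean of both lips).
2. **SAP 10.7.1.** Specify a table of adverse event and ADE incidence by device in the SAF, using the SAP 9.2 assignment rule, with the difference and its 95% interval.
3. **Protocol 6.1.4.** Replace the sentence with: *The differences between the two IMDs in effectiveness and safety will be estimated with 95% CIs (expected half-width about 0.13 for a 90% responder rate with 50 per arm; about 0.12 to 0.18 for adverse device effect incidences of about 9% to 43% with 55 per arm, an assumed range from other indications whose lower end is the filler without lidocaine); no claim of no difference will be made.*

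No test is added, so the change is consistent with protocol 5.2. The cost is a few extra statistics, one table, a more modest claim, a written amendment under protocol section 9 (with ethics committee review if it is judged to affect scientific soundness) and an entry in SAP section 11. No extra subjects or readers are needed.
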